# 19.4. 12-LEAD ECG

Results from the central 12-lead ECG Reading Centre will be included in the reporting of this study. The ECGs will be read and interpreted by the central ECG laboratory. For subjects enrolled before protocol amendment 2, there was an over-night observation period following randomization, and ECGs were collected at multiple timepoints on Day 1 and Day 2 (see below).

- Day 1: Prior to the first dose of study treatment and 2, 4, and 8 hours after the first dose (prior to the second dose), and 10 hours after the first dose (2 hours after the second dose).
- Day 2: Prior to the first dose of study treatment, and 2 and 4 hours after the first dose.

At all other indicated visits after baseline, ECGs were collected once per visit, prior to

administration of the first daily dose of study treatment.

For subjects enrolled after protocol amendment 2, on Day 1, ECG was collected prior to the first dose of study treatment and 2 hours after administration of study treatment. At all other indicated visits after baseline, ECGs were collected once per visit, prior to administration of the first daily dose of study treatment.

The following ECG parameters will be reported for this study on the central read for each safety ECG:

- PR Interval (msec)
- QRS Interval (msec)
- QT Interval (msec)
- QTcF Interval (msec) [derived]
- QTcB Interval (msec) [derived, optional]
- Heart Rate (HR) (bpm)
- Overall interpretation of ECG (Investigator's judgment):
  - Normal
  - Abnormal, Not Clinically Significant (Abnormal NCS)
  - Abnormal, Clinically Significant (Abnormal CS)

The following summaries will be provided by treatment group for ECG data:

- Value and change from baseline by visit (for quantitative measurements)
- Shift in normal/abnormal NCS/abnormal CS from baseline to worst investigator overall interpretation of clinical significance post-baseline
- Shift in markedly abnormal categories from baseline to post-baseline by visit

#### 19.4.1. 12-LEAD ECG: OUTLIER AND MORPHOLOGY ANALYSES

The following Outlier and Morphology findings will be summarized with frequency count and percentage by treatment:

- HR, tachycardic
- HR, bradycardic
- Short PR <120 ms
- Prolonged PR >220ms
- ORS >120 ms
- QT new >500 ms

- QT new > 450 ms (male)
- QT new > 470 ms (female)
- QTcF new >500 ms
- QTcF new >480 ms
- QTcF >30 ms increase from baseline
- QTcF >60 ms increase from baseline
- New atrial fibrillation
- New atrial flutter
- New abnormal U waves
- New ST segment depression changes
- New ST segment elevation changes
- New T wave inverted
- New 2nd degree heart block
- New 3rd degree heart block
- New complete RBBB
- New complete LBBB
- New MI

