#### 8.3.4.6. Electrocardiography

The change from Baseline Descriptive statistics for each of the ECG parameters will be presented by treatment group. The incidence of outlier ECG results will be tabulated. Individual ECG values will be listed by visit and summarized using descriptive statistics. Parameters to be provided on the confirmed read for each safety ECG are HR and the following intervals: RR, PR, QRS, QT, and QTc (QTcF required, QTcB optional). The ECGs will be read and interpreted by the central ECG laboratory. Post-Baseline ECGs for each subject will be compared with the Baseline ECG. Any clinically significant change from Baseline may be recorded as an AE if deemed appropriate by the Investigator, or Investigator in consultation with the Medical Monitor. Outlier analysis will be performed on all subjects with QTcF values greater than 500 ms or change from Baseline > 60 ms in the absence of Baseline ECG abnormalities that preclude accurate surface ECG assessment of ventricular repolarization (eg, bundle branch block).

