#### 4.3. CHANGES TO ANALYSIS FROM PROTOCOL

There are no changes in analysis or definitions from those planned in the final protocol and no changes required due to COVID-19.

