# 7.3. RETESTS, UNSCHEDULED VISITS AND EARLY TERMINATION DATA

For by-visit analyses and summaries of efficacy and safety, data (including scheduled, retests, unscheduled, and early termination) will be assigned to visits after the application of the windowing conventions described in Section 7.4. All measurements will be considered in summaries of abnormalities or worst-case values post-baseline.

In the case of a retest (same visit number assigned), the measurement nearest to the visit date will be used for by-visit summaries. In the case of several measurements equally close to the visit date, the earliest non-missing measurement will be taken. If multiple assessments are available on the same day, then the average of the assessment will be used in the analysis except for laboratory and ECG data, where the assessment at the earliest time of the same day will be used. If both central and local assessments of the same laboratory test are available on the same day, the central assessment will take precedence over the local assessment. Listings will include scheduled, unscheduled, retest and early discontinuation data.

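### The ECG outlier table leaves out the protocol's baseline-ECG condition on the QTcF criteria, and its HR, PR and QRS rows, unlike all the others, carry no baseline condition

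*SAP*

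**What the plan says.** Protocol 8.3.4.6 plans an outlier analysis of QTcF above 500 ms or a change from baseline above 60 ms, "in the absence of Baseline ECG abnormalities that preclude accurate surface ECG assessment of ventricular repolarization (eg, bundle branch block". The same section says that each subject's post-baseline ECGs are compared with the baseline ECG.

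Main Study SAP 19.4.1 lists the findings to be counted by treatment. Both QTcF criteria are there, as "QTcF new >500 ms" and "QTcF >60 ms increase from baseline". Neither 19.4 nor 19.4.1 mentions the baseline condition. SAP 4.3 states: "There are no changes in analysis or definitions from those planned in the final protocol".

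The same list contains rows such as "HR, tachycardic", "Short PR <120 ms" and "Prolonged PR >220ms", with no reference to baseline. SAP 7.3 adds: "All measurements will be considered in summaries of abnormalities or worst-case values post-baseline".

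**The concern.** There are two separate gaps.

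- **QTcF rows.** The protocol restricts which subjects the QTcF outlier analysis applies to. The SAP uses the criteria without the restriction and declares no departure. A programmer working from the SAP would include subjects whom the protocol sets aside.
- **HR, PR and QRS rows.** A subject whose PR was short, or whose QRS was wide, before the first dose can appear under a treatment column although nothing changed.

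Comparing safety with placebo is a primary objective. Heart rate is also the ECG variable that moved in Phase 1: protocol 1.2 and 3.3.1 describe a dose-related rise after single doses and a mean fall of about 10 to 15 bpm at 200 mg tid. Readers will look at the HR rows, and with about 60 subjects per arm a chance imbalance at baseline could blur them.

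**Working it through.** No figure in the plan is at issue, so the main check is textual.

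**Step 1. Classify the rows of SAP 19.4.1.**
- Marked as new: 5 QT and QTcF absolute-limit rows plus 11 rhythm and morphology rows = 16.
- Defined as a change from baseline: QTcF rise above 30 ms and above 60 ms = 2.
- Neither: HR tachycardic, HR bradycardic, PR below 120 ms, PR above 220 ms, QRS above 120 ms = 5.
- Total: 16 + 2 + 5 = 23.

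One consequence is an inconsistency inside the table. A subject with complete bundle branch block at baseline is kept out of the new-RBBB and new-LBBB rows but can still be counted under QRS above 120 ms.

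**Step 2. Compare with other safety sections of the same SAP.** Laboratory results (19.3.1) count as treatment-emergent only if the limit was not crossed at any baseline visit. In vital signs (19.5), the supine/standing blood pressure criteria require a change from baseline, and all potentially significant findings are shown separately for the pre-dose and post-dose periods. The five ECG rows have neither device.

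**Step 3. Test whether the word *new* replaces the protocol condition.** It does not. A subject with bundle branch block and a baseline QTcF below 500 ms can still enter the row for new values above 500 ms. The row for a rise above 60 ms has no filter. If the protocol clause is read as qualifying only the 60 ms criterion, the omission remains for that row.

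**Step 4. See whether the size can be fixed.** The documents give no ECG means, SDs or baseline prevalences, and the readable text gives no HR limits for this table. As an illustration, assume normal values, one baseline and six post-baseline ECGs, within-subject correlation 0.7 to 0.9, no drug effect, HR 70 (SD 10) and PR 155 (SD 20).

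| Row and assumed limit | Above or below limit at baseline | Flagged post-baseline | Share of flagged already met at baseline |
|---|---|---|---|
| HR <60 | 15.9% | 27–37% | 38–56% |
| HR <50 | 2.3% | 5–8% | 21–40% |
| HR <40 (or >100, each) | 0.14% | 0.4–0.6% | 11–29% |
| PR <120 (SAP limit) | 4.0% | 8–12% | 25–44% |
| PR >220 (SAP limit) | 0.06% | 0.2–0.3% | 9–26% |

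The SD of the difference between two arms of 60 in the number meeting the limit at baseline is sqrt(2 × 60 × p × (1 − p)). For p = 0.16 this is sqrt(16.1) = 4.0 subjects. For p = 0.04 it is sqrt(4.6) = 2.1 subjects.

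For PR above 220 ms the model expects only 0.02 to 0.03 pre-existing flagged subjects per arm of 60. If instead a fraction b has a persistent long PR at baseline and a fraction i of the rest develops one, the expected count is 60 × (b + (1 − b) × i):
- b = 1%, i = 2%: 60 × 0.0298 = 1.79, of which 0.60 (34%) are pre-existing.
- b = 5%, i = 1%: 60 × 0.0595 = 3.57, of which 3.00 (84%) are pre-existing.

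For the QTcF exclusion, if 1–2% of subjects have bundle branch block, an arm of 60 contains 0.6 to 1.2 such subjects. These are carriers; fewer would be flagged as outliers.

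The answer therefore runs from almost nothing to several subjects per arm, depending on inputs the documents do not supply.

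**The case against.** The strongest reply has five parts.

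1. *The SAP never says that pre-existing values are counted.* Correct. Section 7.3 mainly settles that retest, unscheduled and early-termination readings enter the summaries; it does not address values abnormal at baseline. The reading is an inference from the contrast between the five rows and the other 18. For HR a baseline element in the intended definition cannot be ruled out, because appendix pages and table templates are not visible.
2. *Baseline status is shown elsewhere.* Largely true. SAP 19.4 gives change from baseline by visit, a shift to the worst investigator interpretation, and a shift in markedly abnormal categories. SAP 19.5 gives change from baseline in heart rate and separate pre-dose and post-dose pulse counts. These would expose a baseline imbalance, but they do not alter the counts in 19.4.1.
3. *There is no systematic bias.* True. Randomisation balances pre-existing findings in expectation, and SAP 19 plans no statistical comparison of safety data by default.
4. *Silence is not removal.* SAP 4.3 could be read as leaving the protocol condition in force. Even so, the section that defines the table does not state it, and the two texts can be programmed differently.
5. *Restricting rows to new findings loses subjects who worsen from an abnormal baseline.* A fair point, which the fix should meet.

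A reader might infer that roughly a third of each arm will be flagged for slow heart rate with no drug effect. The documents do not support this: the 27–37% figure needs an assumed limit of 60 bpm. The only absolute rate limits visible in the SAP are the pulse limits in 19.5 (supine below 40 or at least 100 bpm), and limits of that order give well under 1% per row in the same model.

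**Conclusion.** The point holds as a minor correction to descriptive safety tables. The firmer part is the QTcF condition: the protocol states it, SAP 19.4.1 omits it, and SAP 4.3 declares no change. This needs no assumption. The second part is a well-founded reading of the text for PR and QRS, whose limits are printed, and a weaker one for HR.

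It would go too far to say that the SAP expressly counts pre-existing abnormalities as on-treatment findings, or that the olorinab–placebo comparison is biased. What can happen is added noise in a few counts and a table that does not match the protocol. The size cannot be determined from the documents: every figure above rests on assumed distributions, prevalences or limits. Efficacy analyses are untouched.

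**What to change.** - **QTcF above 500 ms and rise above 60 ms:** apply the baseline exclusion of protocol 8.3.4.6 in SAP 19.4.1 and list which baseline abnormalities trigger it, since the protocol names only one example. Alternatively, declare its removal in SAP 4.3 and show the counts with and without those subjects.
- **HR, PR and QRS rows:** report them as new (limit not met at baseline, met post-baseline). Show subjects who already met the limit at baseline on a separate line, so that worsening from an abnormal baseline is not lost. State the HR limits in 19.4.1, or refer to where they are defined.

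The cost is SAP wording and a baseline flag in the ECG outlier program; no new data are needed. LTE SAP 4.3 records that the Main Study has been analysed. If the tables already exist, the same counts can be added and identified as such in the study report, which Main Study SAP 5.2 already provides for.

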# 3.3. Justification for Dose

# 3.3.1. Main Study

The safety, tolerability, and PK of olorinab have been evaluated in 2 Phase 1 dose escalation studies. Olorinab has also been evaluated in an 8-week Phase 2a, proof-of-concept study in subjects with quiescent to mildly active Crohn's disease. In a single ascending dose study, single oral doses of 10 to 400 mg of olorinab were administered to healthy, adult volunteers. TEAEs were predominantly mild in severity and the majority of TEAEs occurred in subjects administered doses  $\geq$  120 mg. No TEAEs led to discontinuation and there were no serious AEs (SAEs). A dose-dependent trend of increases in supine HR was observed at doses  $\geq$  250 mg. Systemic exposure of olorinab (observed maximum concentration [Cmax] and area under the plasma versus time concentration curve from time zero to the last quantifiable measure [AUCinf]) increased with dose in a manner that was less than dose proportional.

In a multiple ascending dose study, multiple oral doses of olorinab 50, 100, and 200 mg were administered tid for 10 days to healthy, adult volunteers. Most TEAEs were mild in severity. Olorinab was associated with mean decreases from baseline in supine SBP and DBP, respectively, that were evident beginning at 1-hour post-dose on Day 1 and Day 10, in the 100 and 200 mg groups. Blood pressure values returned to baseline or above baseline values upon

discontinuation of treatment. The 200 mg dose was associated with mean decreases in supine HR of approximately 10 to 15 beats per minute (bpm) compared to baseline throughout the Treatment Period. In the 50 mg and 100 mg groups, changes in HR relative to baseline were small and variable.

In a Phase 2a study, doses of 25 and 100 mg of olorinab were administered tid for 8 weeks in a randomized, open-label study in 14 subjects with quiescent to mildly active Crohn's disease. PK results indicated that the systemic exposure of olorinab was dose proportional.

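### The ECG outlier table puts its sex-specific 450/470 ms limits on uncorrected QT, so it counts some slow heart rates as prolongation and has no absolute QTcF row below 480 ms

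*SAP*

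**What the plan says.** Main Study SAP 19.4.1 lists the ECG outlier findings to be counted, with percentages, by treatment. The rows that bear on this point are:

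- Uncorrected QT: the sex-specific rows "QT new > 450 ms (male" and "QT new > 470 ms (female" (each label closes with a bracket), and a further row for new values above 500 ms.
- QTcF, absolute: "QTcF new >480 ms" and "QTcF new >500 ms", the same for both sexes.
- QTcF, change: "QTcF >30 ms increase from baseline" and "QTcF >60 ms increase from baseline".
- Heart rate: separate rows, including "HR, bradycardic".

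SAP 19.4 lists QT and QTcF as separate parameters and marks QTcF as derived. Protocol 8.3.4.6 makes QTcF mandatory and Bazett's correction optional. It defines the outlier analysis on QTcF only (above 500 ms, or a change of more than 60 ms) and names no uncorrected-QT category and no 450/470 ms limits.

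On heart rate, Protocol 3.3.1 reports of the multiple-dose study that "The 200 mg dose was associated with mean decreases in supine HR" of about 10 to 15 bpm. It adds that changes at 50 and 100 mg were small and inconsistent.

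**The concern.** QT depends on heart rate, and QTcF is derived to remove most of that dependence. A fixed limit on QT is therefore a different QTcF limit at every heart rate. At slow rates the 450/470 ms rows count people whose corrected interval is unremarkable. At ordinary and fast rates they pass over people whose corrected interval has crossed the same number. No absolute QTcF row below 480 ms makes up the difference.

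What is at stake is which subjects are counted in the only ECG outlier table that the readable text of either SAP specifies; the LTE SAP (18.4) plans only ECG values by visit. A reader would probably take the 450/470 ms rows as the early signal for repolarisation, and as written they partly measure heart rate.

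**Working it through.** **Inputs.** The limits are those of SAP 19.4.1. The documents name Fridericia's correction but do not print it; the cube-root form is assumed:

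QTcF = QT / (60/HR)^(1/3), so QT = QTcF × (60/HR)^(1/3).

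The documents give no heart-rate distribution, so 40 to 100 bpm is an assumed range. SAP 19.4.1 does not define a new value. It is taken here as a value over the limit when the baseline value was not. The plan states no figure of its own to reproduce.

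**Step 1. What the QT rows mean in QTcF terms.** QTcF (ms) at which each row starts to count:

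| HR (bpm) | Men, QT 450 | Women, QT 470 |
|---|---|---|
| 40 | 393.1 | 410.6 |
| 45 | 408.9 | 427.0 |
| 50 | 423.5 | 442.3 |
| 60 | 450.0 | 470.0 |
| 65 | 462.2 | 482.7 |
| 70 | 473.7 | 494.8 |
| 75 | 484.7 | 506.3 |
| 90 | 515.1 | 538.0 |
| 100 | 533.5 | 557.2 |

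Only at 60 bpm do the rows act as 450/470 ms limits on QTcF. Once the equivalent passes 480 ms, the QT row finds no QTcF value that the 480 ms row does not already count.

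**Step 2. Counted because the heart is slow.** QTcF 420 ms at 48 bpm: QT = 420 × (60/48)^(1/3) = 420 × 1.0772 = 452.4 ms. At 60 bpm the same QTcF gives QT 420 ms, so a fall in rate alone creates a new value in the men's row. With QTcF fixed at 420 ms, the men's limit is crossed below 60 × (420/450)^3 = 48.8 bpm and the women's below 60 × (420/470)^3 = 42.8 bpm.

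**Step 3. Not counted.** A man's QTcF rises from 440 to 468 ms at 75 bpm:

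- QT = 468 × (60/75)^(1/3) = 468 × 0.9283 = 434.5 ms, below 450: no QT row.
- QTcF 468 ms is below 480: no absolute QTcF row.
- The rise is 468 − 440 = 28 ms, not above 30: no change row.

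**Step 4. Bounds of the gap.**

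- Above 480 ms: counted by the QTcF row at any heart rate.
- Rise above 30 ms: counted by the change row at any heart rate.
- At or below 60 bpm: QT is at least as large as QTcF, so a QTcF above 450 or 470 ms also crosses the QT limit and is counted, provided baseline QT was not already over it.
- Above 60 bpm: a QTcF of c escapes a QT limit L from 60 × (c/L)^3 bpm. With c = 480, everything up to 480 ms escapes from 60 × (480/450)^3 = 72.8 bpm in men and 60 × (480/470)^3 = 63.9 bpm in women. Between 60 bpm and those rates, some values escape.

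**Step 5. How narrow it is.** To be new and to have risen by no more than 30 ms, a man with on-treatment QTcF c needs a baseline from c − 30 to 450 ms, a band of 480 − c. At c = 468 the band is 438 to 450 ms (12 ms wide); at c = 478 it is 448 to 450 ms (2 ms). For women the baseline band, c − 30 to 470 ms, is wider, but the on-treatment range is only 470 to 480 ms.

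**The case against.** The strongest reply is that little is lost. Both protocol criteria (QTcF above 500 ms, change above 60 ms) are in the SAP list, so the protocol's commitment is met and the QT rows are extras. QTcF values and changes are summarised by visit, individual ECG values are listed, and a bradycardia row in the same table helps a reader interpret flags at slow rates. The 30 ms change row takes most of the cases one would worry about. All of this stands, and it is why the point is confined to the band in step 4. A reader might infer that the table misses prolonged QTcF below 480 ms in general; it does not.

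A second reply concerns heart rate. A reader might infer from the falls at 200 mg tid that the arms will be distorted differently. The documents do not support that. That dose is four times the top study dose (200/50), changes at 50 and 100 mg were small and inconsistent, the single-dose rises were at 250 mg or more (Protocol 3.3.1), and Phase 2a showed no apparent dose-related change (Protocol 1.2). If heart rate does not differ between arms, rate-driven counts should be roughly balanced. Misclassification of individuals remains, because it needs no drug effect on rate.

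A third reply is that no text says the 450/470 ms limits were meant for QTcF. That is correct; a slip in the row labels is an inference. The point does not need it, because adding QTcF rows closes the gap whatever was intended.

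Finally, SAP 19.4 promises shifts in markedly abnormal ECG categories that the readable text does not define, and some appendix pages are not shown. A lower QTcF category there cannot be excluded.

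**Conclusion.** The point holds in a limited form. As written, the 450/470 ms rows count some slow heart rates as QT prolongation. They leave uncounted new QTcF values above 450 and up to 480 ms (men) or above 470 and up to 480 ms (women) when the rise is 30 ms or less and the heart rate is above 60 bpm and high enough to keep QT under its limit. The escape is complete from about 73 bpm in men and 64 bpm in women.

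This rests on Fridericia's formula, the assumed meaning of a new value, and assumed heart rates. The number of affected subjects among the planned 240 cannot be estimated from the documents.

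The consequence is confined to a descriptive safety table; no efficacy result, sample size or error rate changes. Safety is a primary objective, so a reader might infer that a primary endpoint is compromised. However, the primary safety endpoint names adverse events, vital signs and laboratory results, not ECG (Protocol 8.3.1.1). The change is worth making because it is nearly free and alters which subjects the table counts.

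**What to change.** In SAP 19.4.1, either apply the two sex-specific rows to QTcF, or leave them and add rows for new QTcF above 450 ms in men and above 470 ms in women. The second option avoids any assumption about what the limits were meant for. Keep the uncorrected QT row above 500 ms if wanted. State what makes a value new, and confirm whether the markedly abnormal categories in SAP 19.4 already include a QTcF limit below 480 ms.

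The cost is two table rows using a variable already derived, with no new data. LTE SAP 4.3 records that the Main Study analysis has been completed, so rows added now should be identified in the study report as unplanned, as Main Study SAP 5.2 requires.

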### 19.5. VITAL SIGNS

Orthostatic vital signs (VS) include the collection of blood pressure (BP) and HR after the subject has been resting in the supine position for at least 5 minutes and then again after 1 and 3 minutes of standing. For subjects enrolled before protocol amendment 2, there was an over-night observation period following randomization, and the orthostatic VS were collected at multiple timepoints on Day 1 and Day 2 (see below).

- Day 1: Prior to the first dose of study treatment and 2, 4, 8 hours after the first dose (prior to the second dose), and 10 hours after the first dose (2 hours after the second dose).
- Day 2: Prior to the first dose of study treatment and 2 and 4 hours after the first dose.

At all other visits after baseline, orthostatic vital signs were collected once per visit, prior to administration of the first daily dose of study treatment. For Day 1 and Day 2, the assessment at the earliest time of the same day will be used for analysis.

For subjects enrolled after protocol amendment 2, orthostatic BP and HR assessments were collected once per visit, prior to administration of the first daily dose of study treatment for the post-baseline visits.

The following VS data will be summarized using descriptive statistics by treatment group as well as for active treatment groups pooled.

- The actual measurement values of vital signs (BP and HR at Supine, Standing 1 and 3 minutes) at each visit/timepoint
- Change from baseline for orthostatic VS (BP and HR at Supine, Standing 1 and 3 minutes): calculated as post-baseline values minus the value prior to the first dose on Day 1.
- Change from supine to standing in orthostatic vital signs (BP and HR): calculated as the standing measurement minus the supine measurement by visit/timepoint. It will be calculated for 1-minute standing and 3-minute standing separately.

Body temperature and respiratory rate were collected once per visit, prior to the administration of the first daily dose of study treatment (for visits occurring during the Treatment Period). Change from baseline will be summarized in a similar manner. Baseline is defined as the last measurement collected before the first dose on Day 1.

Vital sign values meeting the criteria as defined in

Table 2 below will be categorized as potentially clinically significant (PCS) findings. These findings will be summarized with frequency count and percentage for each treatment as well as for the active treatments pooled, both overall and by visit for the pre-dose period (including Screening, Run-in and Day 1/Pre-dose) and for the post-dose period The summaries and counts will be presented at both the subject level (counting subjects with PCS findings) and event level (counting all PCS events).

Table 2: Vital Sign PCS Criteria

Parameter	PCS Category	PCS Criteria
Systolic BP (mm Hg)	High	(> 155 Standing or $\geq$ 140 Supine) and Supine increase from baseline $\geq$ 20
	Low	( $\leq$ 80 Standing or $\leq$ 90 Supine) and Supine decrease from baseline $\geq$ 20
Diastolic BP (mm Hg)	High	(> 105 Standing or ≥ 90 Supine) and Supine increase from baseline ≥ 15
	Low	(< 35 Standing or < 40 Supine) and Supine decrease from baseline ≥ 15
Pulse Rate (bpm)	High	≥ 120 Standing or ≥ 100 Supine
	Low	< 40 Standing or Supine
Orthostatic Systolic BP (mm Hg)	Low	Supine to Standing decrease ≥ 20

Page 57 of 77

Parameter	PCS Category	PCS Criteria
Orthostatic Diastolic BP (mm Hg)	Low	Supine to Standing decrease ≥ 10
Orthostatic Pulse Rate (bpm)	High	Supine to Standing increase ≥ 30
Dagnizatory Data (homm)	High	≥ 28
Respiratory Rate (brpm)	Low	≤8
Tamparatura (°C)	High	> 38
Temperature (°C)	Low	< 35

Abbreviation: bpm = beats per minute; BP = blood pressure; brpm = breaths per minute; PCS = potentially clinically significant.

Note: Standing is from Standing 1 or Standing 3 measurement.

